Through workshops and ongoing supervision/consultation, we will train peer leaders to competently deliver both versions of MI and conduct a randomized controlled trial comparing the two versions of MI to enhance treatment engagement in SGM male survivors with mental health problems. All SGM male survivors who meet inclusion criteria, including significant emotional distress, will complete pre-test measures and be randomized to 6-week traditional MI delivered by peers in online groups or 6-week MI with trauma-informed, SGM affirmative care delivered by peers in online groups. Randomization will be counterbalanced by treatment status: treatment naive versus treatment-experienced (prior treatment but not within the past 60 days). This same procedure of counterbalancing by treatment status was previously used in the randomized controlled trial of MI (Burke et al., 2003) to help Iraq and Afghanistan veterans with mental health difficulties engage in more mental health services. Participants will complete pre-intervention (baseline), end of the 6-week intervention, 60- and 120-days follow-up assessments via an online survey platform, to determine if there was an increase in formal mental health treatment engagement, and any significant changes in mental health symptomology (i.e., PTSD, depression, high-risk drinking, and

illicit substance use). Peer leaders will co-facilitate groups throughout the study. It is anticipated that a peer leader will run between 1-3 groups throughout the study.

Parent Study Screening and Participant Eligibility Criteria.

Once recruitment advertisements are posted on the various websites (listed in detail below), those interested in finding out more information, will be directed to a website that contains the informed consent and Frequently Asked Questions about participation. Participants will then be asked to complete a short questionnaire including demographic questions with their contact information to be sent to a member of the research team to set up a screening appointment via telephone with the interested participant.

Screening

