Demographics and SGM Identification. Participants will be asked about their age, gender at birth, current gender identification, race/ethnicity, sexual orientation, marital status, highest level of education, and employment status at screening. Participants will also be asked about their treatment status to ensure eligibility (not currently in mental health treatment and/or have not been in treatment for past 60 days). Across post-interventions and follow-ups, participants will be asked if there are any changes to their employment, education, or marital status.

Sexual Abuse Characteristics. Participants will be asked about the age of onset of sexual abuse; type of abuse (e.g., penetration, non-penetration); number of perpetrators; relationship to their perpetrator(s); and the frequency of the abuse. Participants will also be asked if someone had found out about the abuse while it was occurring, and if they received any kind of psychotherapy or counseling as a result.

Current Experiences of Distress will be measured using the ***Center for Epidemiological Studies Depression Scale (CES-D; Radloff, 1977)***, a 20-item questionnaire that asks about experience and frequency of depressive symptoms over the past week. A score of 16 or higher identifies those individuals who are at risk for major depression. This score will be used as our cutoff for inclusion in the study.

Life Events Checklist (Blake et al., 1995) is a self-report measure that screens for 16 potentially traumatic events across individuals' lifetimes. Participants note whether the event happened to them personally, they witnessed it happen to someone else, they learned about it happening to someone close to them, or if it does not apply or does not fit.

MINI (Sheehan et al., 1998) is a structured interview that takes approximately 15-20 minutes to administer. The MINI is used extensively in research studies to make fairly quick and accurate diagnoses of psychiatric disorders and will be used here to assess, in part, for exclusion criteria.

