Those participants who meet inclusion criteria will be provided a link to the online surveys for baseline assessment. Measures will include prior and current mental health treatment engagement, barriers and beliefs around seeking formal mental health treatment, as well as measures assessing symptomatology (e.g., substance use, depression, PTSD). At the completion of the 6-week group, participants will complete post-intervention assessments and 60- and 120-day follow-up assessments on the various outcome measures. A summary of the timing and purpose of assessments is shown in Table 1.

Baseline, Post-Intervention and Follow-up Outcomes

Primary Outcome: Mental Health Treatment Engagement. The primary outcome here will be the binary distinction between those who initiated mental health treatment/reinitiated mental health treatment versus those who did not. Mental health treatment engagement will be operationally defined as having ≥ 1 visit(s) or scheduled appointments to any mental health services within 120 days of the last online group.

Primary Outcome: Depression. Center for Epidemiological Studies Depression Scale (CES-D; Radloff, 1977) is a 20-item questionnaire that asks about experience and frequency of depressive symptoms over the past week. A score of 16 or higher identifies those individuals who are at risk for major depression.

Secondary Outcome(s): will include PTSD, alcohol and drug abuse, quality of life, and service utilization.

PTSD Checklist for DSM-5 (PCL-5; Weathers et al., 2013) is a 20-item instrument that corresponds to the current psychiatric diagnostic criteria for PTSD.

Alcohol, Smoking and Substance Involvement Screening Test (ASSIST; WHO ASSIST Working Group, 2002; Humeniuk et al., 2008) is an 8-item measure of participants’ use of alcohol, tobacco products, and other drugs across their lifetime and in the past three months.

Inventory of Psychosocial Functioning (IPF-B; Rodriguez, Holowka, & Marx, 2012) is a brief 7-item scale that assesses functional impairment or quality of life related to trauma and PTSD.

The Service Use and Resource Form (SURF; Rosenheck et al., 2016) is a questionnaire assessing current living situation, use of inpatient and outpatient mental health and alcohol or drug treatments, psychotropic medication use, and use of other support services. The SURF will be administered during screening, baseline, post-intervention and follow-up.

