Fidelity monitoring will occur ad hoc by independent raters using audio-recordings of intervention sessions. At least 30% of the sessions (traditional MI and trauma-informed MI) will be coded ($n = 90$). Three coders will rate each session. [name] will host a training with the raters to familiarize them with the rating scales and interventions. The three raters will conduct the fidelity ratings over a six to eight month period (approximately) between June 2021 and February 2022. The three raters ([name], [name] and [name]) have previous experience conducting this task and will be supervised by [name]. Audio recordings of selected group sessions will be sent to the raters using Yale's secure file transfer (FileLocker).

Assessment Measures. Peer specialists will also be asked to complete a reflective journaling exercise (see attached) after each treatment cycle they co-facilitate. In addition, they will complete several assessments measures (see attached) prior to their attendance at the MI training then again after they attend the MI training. Peer specialists will be asked to answer approximately three open-ended questions at the end of the study.

Table 1: Assessment Schedule

Assessment Name		Screening	Baseline	Post-intervention	60-Day Follow-up	120-Day Follow-up
Peer Specialists	Independent Tape Rater Scale			x		
Male Survivors	Demographic and SGM identification	x	x	x	x	x
	Sexual abuse characteristics	x				
	Life Events Checklist	x				
	Mini International Neuropsychiatric Interview	x				
	Telephone-Assessed Mental State (TAMS)	x				
	Columbia-Suicide Severity Rating Scale (C-SSRS)	x	x	x	x	x

Brief Dissociative Experiences Scale (DES-B Modified for DSM-5)		x	x	x	x
Center for Epidemiological Studies-Depression Scale	x	x	x	x	x
PTSD Checklist for DSM-5		x	x	x	x
Alcohol Smoking and Substance Involvement Screening Test (ASSIST)		x	x	x	x
Inventory of Psychosocial Functioning		x	x	x	x
Barriers to Help Seeking Scale		x	x	x	x
Conformity to Masculine Norms Inventory		x	x	x	x
Minority Stress Scale		x	x	x	x
Working Alliance Inventory			x		
Service Use and Resource Form (SURF)	x	x	x	x	x
Adult Resilience Measure – Revised (ARM-R)		x	x	x	x

Participant Population: Provide a detailed description of the types of participants who will be recruited into this study.

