Webber, K. H., Tate, D. F., Quintiliani, L. M. (2008). Motivational interviewing in internet groups: a pilot

study for weight loss. *J Am Diet Assoc*, 108(6),1029-32.

West, D. H., Harvey, J. R., Kruckowski, R. A., Prewitt, T. E., Priest, J., & Ashikaga, T. (2016). Do individual online motivational interviewing chat sessions enhance weight loss in a group online weight control program? *Obesity*, 24(11), 2234-2340.

Westra, H. A., Aviram, A., & Doell, F. K. (2011). Extending motivational interviewing to the treatment of major mental health problems: Current directions and evidence. *Canadian Journal of Psychiatry*, 56(11): 643-650. Doi: 10.1177/070674371105601102

WHO ASSIST Working Group. (2002). The Alcohol, Smoking and Substance Involvement Screening Test (ASSIST): development, reliability and feasibility. *Addiction*, 97(9), 1183-1194.

Williams, J. K., Kisler, K. A., Glover, D., & Sciolla, A. (2011). *Exploring childhood sexual experiences and vulnerability to intimate partner violence among African American MSMW: Was that abuse or love?* New York: Nova Science Publishers.

Analysis Plan

To assess the success of randomization, baseline demographic and clinical characteristics, the two randomized groups were compared using chi-square tests for categorical variables and t-tests or Mann-Whitney tests for continuous variables. Data analyses were conducted on the intent-to-treat sample. All variables were evaluated for their distributional properties and data processing errors. Robust estimators were used to address non-normal data.

Variables were assessed for amount and pattern of missing data. Full information maximum likelihood estimation was used in subsequent analyses to address missingness. Inclusion of informative variables were included as needed. Analyses were conducted in SPSS 28.0 (IBM, 2021). For outcome analyses, linear mixed models (LMM) of mental health symptoms were modeled as a repeated measures outcome variable, nested within participants. Baseline demographic, clinical variables, and sexual abuse experiences were included as time-invariant covariates (between participants), as was treatment group. Thus, for each outcome, the primary analysis included all observations nested in persons and cohorts, controlling for baseline clinical and demographic variables.

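### The Analysis Plan gives the screening CES-D no role beyond eligibility, so precision on the CES-D primary outcome may be lost

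*Combined protocol and SAP*

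**What the plan says.** The Outcomes part of the Research Plan (Section IV, item 3) lists "Primary Outcome: Depression. Center for Epidemiological Studies Depression Scale" as one of two primary outcomes. In Table 1 (Assessment Schedule) the row "Center for Epidemiological Studies-Depression Scale" is marked in all five columns, with screening and baseline as separate visits.

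The two visits differ in purpose, and both come before allocation:
- **Screening.** A CES-D of 16 or more is required for entry: "This score will be used as our cutoff for inclusion in the study".
- **Baseline.** It follows once eligibility is settled: "Those participants who meet inclusion criteria will be provided a link to the online surveys for baseline assessment".
- **Randomisation.** It comes after the baseline measures: eligible men "will complete pre-test measures and be randomized to 6-week traditional MI" or to the tailored version.

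On covariates the Analysis Plan says: "Baseline demographic, clinical variables, and sexual abuse experiences were included as time-invariant covariates (between participants), as was treatment group". On the data in the model it says that "the primary analysis included all observations nested in persons and cohorts, controlling for baseline clinical and demographic variables". Beyond the general phrase "controlling for baseline clinical and demographic variables", it does not list the clinical covariates, does not say whether baseline CES-D is one of them, and does not say which visits are outcome rows. The screening CES-D is not mentioned.

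**The concern.** A single past-week depression score is a noisy reading of a man's usual level. A second reading before randomisation may help to predict his follow-up score. Every randomised man has one by design, because he could not be enrolled without it. If the model ignores it, the standard error of the CES-D comparison may be larger than it needs to be, with nothing saved in data collection.

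The plan also leaves open whether baseline CES-D is a covariate, an outcome row or both. That choice decides whether the screening score can help at all.

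**Working it through.** **The plan's own figure.** Section V, item 4 gives 137 completers per group (274 in all) for an effect size of .35, power .80 and alpha .05. A plain two-sided comparison of means gives 2 × (1.960 + 0.842)² / 0.35² = 128.2, so 129 per group. At 137 the power is about .82. The dropout step agrees: 274 / 0.8 = 342.5, or 344 as an even number. The 137 therefore does not follow exactly from its stated inputs. That is a separate matter, and 274 serves below only as a scale.

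**Inputs.** From the documents: entry at CES-D 16 or more, and 274 completers. Assumed, because the documents give no values: source-population CES-D mean 16 to 24, SD 11 and normality; screening-baseline correlation (S–B) .6 to .8; correlations with one follow-up score (S–Y, B–Y) .5 to .7.

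**Formulas**, in SD units before selection:
- Residual variance of Y given B and S is 1 − R², with R² = (BY² + SY² − 2·BY·SY·SB) / (1 − SB²). Selection on S does not change it.
- Let k be the fraction of the variance of S removed by the cut-off: k = 0.637 for source mean 16 (cut at the mean) and 0.450 for mean 24 (cut 0.727 SD below it).
- After selection, Var(B) = 1 − k·SB², Var(Y) = 1 − k·SY² and Cov(B,Y) = BY − k·SB·SY. Residual variance of Y given B alone is Var(Y) − Cov² / Var(B).

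**Worked case**, all correlations .6 and mean 16. R² = (0.36 + 0.36 − 0.432) / 0.64 = 0.45, so 0.550 remains with both scores. With baseline alone: Var(B) = Var(Y) = 1 − 0.637 × 0.36 = 0.771 and Cov = 0.6 − 0.229 = 0.371, giving 0.771 − 0.371² / 0.771 = 0.592. The fall is 1 − 0.550 / 0.592 = 7.2%. At mean 24 it is 1 − 0.550 / 0.609 = 9.7%.

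Extra completers equal 274 / (1 − fall) − 274. For 9.7% that is 303.4 − 274 = 29.

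| S–B | S–Y | B–Y | Fall in residual variance, source mean 16 to 24 | Equivalent completers |
|---|---|---|---|---|
| .6 | .6 | .6 | 7.2% to 9.7% | 21 to 29 |
| .8 | .7 | .7 | 6.8% to 8.5% | 20 to 25 |
| .8 | .6 | .6 | 3.9% to 4.9% | 11 to 14 |
| .8 | .55 | .6 | 1.3% to 1.7% | 4 to 5 |
| .7 | .5 | .6 | 1.0% to 1.4% | 3 to 4 |
| .7 | .5 | .7 | 0.02% to 0.03% | 0 |
| .8 | .56 | .7 | 0% | 0 |

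The last row is exactly zero because .56 = .8 × .7: screening then predicts follow-up only through baseline.

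The top of the table is a working figure, not a bound. With all three correlations at .7 the same formulas give 9.7% to 12.6%. With S–B .6 and both others .7 they give 13.0% to 17.2%, but there screening tracks follow-up better than it tracks baseline. Averaging three follow-up visits also raises the gain: with all correlations .6, Var(Y) starts at (1 + 2 × 0.6) / 3 = 0.733 and the fall is 13.0% to 17.2%.

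**Role of the baseline score.** The table treats baseline CES-D as a covariate. If it is instead the first outcome row and the effect is an unconstrained condition-by-time term, a covariate that is constant within a man cancels from his change scores. In a simulated mixed model with complete data, the standard error of that term was 0.9747 with the screening score and 0.9747 without it.

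**The case against.** The strongest reply is that this is an optional refinement of ordinary practice. Adjusting for one pre-randomisation value is common, no bias or type I error problem follows, and the documents hold no figure from which a loss can be established. All of that stands. An older score usually predicts follow-up less well than a newer one, and the table's low rows show how quickly the gain then disappears.

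Four stronger readings are tempting and are not supported:
- **That the plan excludes the screening score.** It does not. Sexual abuse characteristics are collected at screening only (Table 1) and are in the model. The plan also has an open provision for further informative variables and refers to all observations. The use of screening CES-D is unspecified. Even so, the open provision names no variable and fixes nothing in advance.
- **That standard errors are certainly too large.** This depends on correlations the documents do not give, and the loss may be nil.
- **That the gain holds whatever role baseline CES-D has.** It does not, as the condition-by-time check shows.
- **That the trial as a whole would gain.** The binary engagement outcome is untouched, and variance between the online groups is not reduced.

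**Conclusion.** The point holds as a possible loss of efficiency on one of the two primary outcomes. Two pre-randomisation CES-D scores are scheduled, and the plan states no role for the first beyond eligibility. The further fall in single-visit residual variance is about 0% to about 10%, or 0 to about 30 completers on 274. This rests on the assumed correlations, SD 11, source mean 16 to 24, normality and truncation at 16. It also requires baseline CES-D to be a covariate, or the arms to be constrained equal at baseline. Nothing here suggests bias.

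**What to change.** Add to the Analysis Plan:

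> *The CES-D model uses the post-intervention, 60-day and 120-day scores as outcome rows, and includes both the screening and the baseline CES-D totals as fixed, pre-specified covariates; neither pre-randomisation score is an outcome row.*

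The last clause matters. Without it, a plan that takes in all observations could place baseline CES-D on both sides of the model, or admit as an outcome a screening score truncated at 16.

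The cost is one sentence and one degree of freedom for the added covariate, with no new data. The Analysis Plan is written in the past tense. If the analysis is already complete, report this model as a labelled sensitivity analysis beside the original and do not present it as pre-specified.

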a. Targeted for enrollment at Yale for this protocol: 356 for the online groups.

b. If this is a multi-site study, give the total number of participants targeted across all sites.

4. How was this estimate derived?

Because this study examines repeated measures outcomes with the two treatment conditions, assigned at the individual level, power analysis makes several assumptions: continuous outcomes, a linear link function, random effects covariance structure, and homogeneous covariance structure (within treatment groups). These analyses also assume testing for HTE effects. Conservatively assuming an effect size of .35, with a power of .80 and an alpha of .05, 137 subjects per group would be required. This represents a total completed sample of 274. Assuming a dropout rate of 20% (rounded up to 70, for nearest multiple of 2), this requires a recruited sample of at least 344. In a meta-analysis of 72 clinical trials, the initial effect size, that is 1-month post-intervention, was quite high ($d = .77$). However, the strength of the effect decreased over time, with effect sizes of .39 at 1-3 months, and .31 at 6-12 months.

5. Process of Consent/Accent (*NOTE: When a study includes minors, parent provide permission [not consent] for the child's participation, and the child provides assent for participation*)

Informed consent is an ongoing process that is best suited by transparency and openness to participants. Thus, participants will give consent in the initial online screening contact form and verbally in the screening call. Participants will be provided with information about the nature of the study, as well as the expected time and energy commitment required to complete the assessments. It will also be explained to participants that they are consenting to be randomly assigned to one of two MI interventions (with brief explanation about content as well as frequency and length of sessions).

Participants will be asked to provide informed consent online, prior to completing in the screening questionnaires. Consent will be required in order to access the assessment measures. If a participant does not provide consent, they will not engage in the screening assessment or be enrolled in the study.

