Before examining the potential role of any mediators, LMM was conducted to determine any main or interaction effects condition and/or time may have had on these mediators as outcomes. To assess heterogeneity of treatment effects, the potential moderating impact that participant demographic variables and significantly correlated covariates had on the relationship between condition and primary outcomes was examined by including a moderator x condition interaction term in models.

Inclusion of demographic and clinical variables in mixed models allowed for testing of heterogeneity of treatment effects (HTE), with adjusted *p*-values. Specifically, in addition to the primary analyses, subsequent supplementary analyses tested potential moderators by including a treatment group X demographic interaction (race, comorbidity, and education) as these are the most likely candidates for HTE effects. Potential moderating effects of baseline values of minority stress, conformity to masculine norms and barriers to help seeking were also examined using SPSS PROCESS, which provides estimates of conditional effects of focal predictor (treatment condition) at different values of the moderator.

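### Moderation by minority stress, masculine norms and help-seeking barriers is assigned to SPSS PROCESS, which by itself provides none of the FIML, repeated-measures or cohort structure that the Analysis Plan commits to.

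*Combined protocol and SAP*

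**What the plan says.** All of the text is in the Analysis Plan at the end of the combined protocol and SAP.

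- Population: "Data analyses were conducted on the intent-to-treat sample".
- Missing data: "Full information maximum likelihood estimation was used in subsequent analyses to address missingness". No exception is made for moderation analyses.
- Structure: for each outcome, "the primary analysis included all observations nested in persons and cohorts".
- Moderation in general: the influence of demographics and correlated covariates "was examined by including a moderator x condition interaction term in models".
- Race, comorbidity and education: treatment-by-covariate interactions in mixed models, with adjusted p-values.
- The three psychological scales, at their baseline values, "were also examined using SPSS PROCESS, which provides estimates of conditional effects of focal predictor (treatment condition) at different values of the moderator". That output is the only reason given for the choice of tool.

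For the PROCESS step the plan names no outcome, time point, missing-data method, person or cohort term, or p-value adjustment.

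**The concern.** The three scales are the moderators closest to what the tailored arm adds. The Research Plan (Section IV) says that its extra modules address minority stress and traditional masculinity, and its fidelity items include reframing help-seeking. Yet these moderators are given to a different tool from the rest of the heterogeneity analysis. The documents do not describe how PROCESS works. I take it as known that it fits ordinary or logistic regression with one record per person, deletes incomplete records by default, and fits neither random effects nor FIML.

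Followed as written and with nothing added, the plan therefore gives these moderators a weaker analysis than it promises elsewhere. Their results could differ from the mixed-model results for technical reasons alone. The output most exposed is the set of conditional treatment effects, which is what the plan cites PROCESS for.

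**Working it through.** **Inputs from the documents.** 356 men randomised; closed groups of about 8 to 10; post-baseline assessments at the end of the intervention, 60 and 120 days (Section IV, Research Plan). Effect size 0.35, power 0.80, alpha 0.05, 137 per group, 274 completers, 20% dropout, at least 344 recruited (Section V, item 4).

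**Inputs assumed.** Two-sided alpha; intraclass correlation (ICC) for the online group of 0.01 to 0.10; correlation between visits of 0.5 to 0.7. The documents give none of these.

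**1. The plan's own figures.** The plan states: "Conservatively assuming an effect size of .35, with a power of .80 and an alpha of .05, 137 subjects per group would be required". A simple two-group comparison gives n = 2(1.960 + 0.842)² / 0.35² = 128.1, so 129 per group (130 by t-test). With 137 per group, power is about 0.82 to 0.83. The plan says its figure allows for repeated measures and heterogeneity testing but gives no inputs for either. So 137 is not reproduced exactly, is on the cautious side, and cannot be called wrong. The dropout step agrees within rounding: 274 / 0.80 = 342.5, so 343 against 344. This point disputes none of these figures.

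**2. Missing outcomes, single-visit complete-case analysis.**
- Men retained: 356 × 0.80 = 284.8, about 285. Men lost: 356 − 285 = 71.
- Standard error ratio: √(356 / 285) = 1.118, about 12% larger.
- Detectable condition-by-moderator effect (80% power, per SD of moderator): (1.960 + 0.842) × 2 / √N. This is 0.297 SD at N = 356 and 0.332 SD at N = 285.

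These are upper bounds on the loss. A mixed model gains from men with some follow-up visits, but almost nothing from men with none. The documents do not say how the 20% divides between the two.

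**3. Repeated measures (symptom outcomes only).** The variance of a three-visit mean relative to one visit is (1 + 2ρ) / 3, which is 0.67, 0.73 and 0.80 at ρ = 0.5, 0.6 and 0.7. It applies only if the target is the average over follow-up and all visits are present.

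**4. Clustering and the conditional effects.** Design effect = 1 + (m − 1) × ICC. True error of a nominal 5% test = 2[1 − Φ(1.960 / √design effect)].

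| Group size m | ICC | Design effect | True error |
|---|---|---|---|
| 8 | 0.01 | 1.07 | 5.8% |
| 9 | 0.02 | 1.16 | 6.9% |
| 9 | 0.05 | 1.40 | 9.8% |
| 9 | 0.10 | 1.80 | 14.4% |
| 10 | 0.10 | 1.90 | 15.5% |

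A simulation of single-level regression (40 groups of 9, 20% random loss, 4,000 runs) gave 6.4%, 9.0% and 13.1% at ICC 0.02, 0.05 and 0.10. These are slightly below the formula because the loss shrinks the groups.

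**5. Clustering and the interaction test.** In the same simulation the condition-by-moderator test rejected in 4.5% to 5.9% of runs when the moderator's slope was the same in every group. It rose to 8.9% to 10.8% only with an assumed between-group slope variance of 0.05.

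**The case against.** The strongest reply is that the documents nowhere say that men are dropped or nesting ignored. On its face the FIML sentence covers later analyses, and imputation or cohort indicators used as covariates are not ruled out. This stands: the loss of data and of clustering is inferred from how the tool works. It does not close the gap, because the named tool does not do FIML and the plan describes no step that would supply it.

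Second, the word *also* may mean that PROCESS supplements interaction terms already fitted in the mixed models. The text allows that reading. Even so, the conditional effects would come from PROCESS without the stated structure.

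Third, engagement is a single binary outcome per man, so the repeated-measures point does not apply to it. This stands in full.

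Fourth, the loss is modest and partly foreseen: 285 exceeds the 274 completers on which the trial was sized. This also stands.

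A reader might go further and infer that these analyses abandon intention to treat, or that the interaction tests are badly anticonservative. Neither is supported. Men analysed with complete data are still analysed as randomised, so any loss is a missing-data matter. The interaction test holds its level unless moderator slopes vary between groups.

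**Conclusion.** The point holds as an unreconciled conflict between the Analysis Plan's general commitments and the tool it names for three moderators.

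- Symptom outcomes such as the CES-D: PROCESS in its ordinary form leaves out partial follow-up data (at most about 71 of 356 men for a single-visit analysis) and the remaining visits.
- All outcomes: the conditional treatment effects carry a true error of about 6% to 15% where 5% is claimed.

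The second range rests on assumed ICCs, and on clustering by the closed online group, which I take to be what the plan means by cohort. These are secondary heterogeneity analyses. It would be wrong to infer that the primary treatment comparison is compromised, since it is specified with the full nested structure.

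**What to change.** Fit each baseline moderator × condition (× time) term in the mixed model used for the primary symptom analysis. For engagement, use a logistic model with a cohort term. Take the effects of condition at chosen moderator values from those models, and apply the same p-value adjustment as for race, comorbidity and education. If PROCESS results are kept, label them supplementary and state their outcome, time point, missing-data method and handling of cohort.

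The cost is revised syntax and a few lines of text; no new data are needed. The Analysis Plan is written in the past tense, so if results are already known the change must be labelled a reanalysis.
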